7.1. Treatments Administered

This study involves 3 parallel treatment arms: PRCL-02 Dose 1, PRCL-02 Dose 2, and placebo. All patients will receive study drug, to be administered orally once daily, for 12 weeks.

The planned doses are:

PRCL-02 Dose 1: Loading dose of 150 mg followed by a once daily maintenance dose of 25 mg, commencing on Day 2 and continuing for 12 weeks.

PRCL-02 Dose 2: Loading dose of 300 mg followed by a once daily maintenance dose of 50 mg, commencing Day 2 and continuing for 12 weeks.

Doses may be revised upwards or downwards based on new safety information and exposure data becoming available during the course of the study.

The drug product is composed of PRCL-02 and inactive ingredients. Matching placebo will consist of only the inactive ingredients. PRCL-02 or placebo will be provided as tablets of 25 mg or 50 mg conditioned in blister packs.

The investigator or his/her designee is responsible for the following:

- explaining the correct use of study drug to the patient
- verifying that instructions are followed properly
- maintaining accurate records of study drug dispensing and collection
- at the end of the study returning all unused medication to PRCL Research Inc., or its designee, unless the sponsor and sites have agreed all unused medication is to be destroyed by the site, as allowed by local law

7.1.1. Packaging and Labelling

PRCL-02 and placebo will be provided as tablets in blister packs. The sponsor or its designee will provide sufficient quantities of PRCL-02 drug products to allow completion of this study. PRCL-02 drug products are manufactured, tested, packaged, and labeled in accordance with all applicable good manufacturing practice requirements, guidelines, and regulations, and will be labeled according to the country's regulatory requirements. A certificate of release confirming that study drugs are to be used "for human use in clinical study" will be supplied. PRCL-02 drug products are for investigational use only and are to be used only within the context of this study.

7.2. Method of Treatment Assignment

Patients who meet all criteria for enrollment will be randomized in 1:1:1 to 1 of 3 treatment arms: PRCL-02 Dose 1, PRCL-02 Dose 2, or placebo. Assignment to treatment groups will be determined by a computer-generated random sequence using an interactive web-response system (IWRS). The IWRS will be used to assign blister packs containing double-blind drug product to each patient. The IWRS system will be programmed to balance the treatment arms according to

weight (<95kg and \geq 95kg), and prior number of failed therapies (<3 and \geq 3). The purpose of the algorithm is to maintain approximately the same proportion of patients for these variables in each treatment arm.

During the patient's dispensing visits, the site will access the IWRS for the correct blister pack number to dispense. The drug product will be dispensed in a kit, which will provide amounts of treatment consistent with the dispensing plan (Section 7.1) and the allowed window period (Table PRCL 1). The patients will be provided with sufficient treatment to last until the next dispensing visit. (Table PRCL 1).

7.2.1. Selection and Timing of Doses

Patients should take their medication at approximately the same time in the morning everyday. It is recommended (but not required) that the dose should be taken with food.

On days when there is pre-dose PK sampling (at 1 week, 2 weeks, 4 weeks, 8 weeks and 12 weeks after the first dose), the dose must be administered at the site after the pre-dose sample has been obtained. On all other days, patients must take their study drug at approximately the same time in the morning. It is recommended (but not required) that the dose should be taken with food. The study drug (tablet) should be swallowed whole, and should be taken with a glass of water.

7.3. Blinding

This is a double-blind study; both patients and investigators will be blinded.

To preserve the blinding of the study, no study personnel will see the randomization table and treatment assignments before database lock.

Emergency unblinding for AEs may be performed through the IWRS, or other means if necessary. Emergency unblinding may be used ONLY if the patient's well-being requires knowledge of the patient's treatment assignment.

If an investigator, site personnel performing assessments, or patient is unblinded, the patient must be discontinued from the study, unless there are ethical reasons for the patient to remain in the study. In cases where there are ethical reasons to have the patient remain in the study, the investigator must obtain specific approval from the sponsor designated medical monitor for the patient to continue in the study.

In case of an emergency the investigator should contact the sponsor designated medical monitor prior to unblinding a patient's treatment assignment. However, the investigator has the sole responsibility for determining if unblinding of a patient's treatment assignment is warranted for medical management of the event. The patient safety must always be the first consideration in making such a determination. If a patient's treatment assignment is unblinded, the sponsor must be notified immediately. If the investigator decides that unblinding is warranted, it is the responsibility of the investigator to promptly document the decision and rationale and notify the sponsor as soon as possible.

7.4. Dosage Modification

Not applicable.

7.5. Preparation/Handling/Storage/Accountability

All PRCL-02 drug products will be stored in a secure and locked area with strictly limited access and monitored for temperature, and allocated and dispensed by appropriately trained personnel. Study drugs will be stored between 2°C to 8°C.

The investigator or his/her designee is responsible for the following:

- confirming appropriate temperature conditions have been maintained during transit for all study treatment received and any discrepancies are reported and resolved before use of the study treatment.
- ensuring that only participants enrolled in the study may receive study treatment and only authorized site staff may supply or administer study treatment. All study treatments must be stored in a secure, environmentally controlled, and monitored (manual or automated) area in accordance with the labeled storage conditions with access limited to the investigator and authorized site staff.
- the investigator, institution, or the head of the medical institution (where applicable) is responsible for study treatment accountability, reconciliation, and record maintenance (such as receipt, reconciliation and final disposition records).

7.6. Treatment Compliance

Patient compliance with study drug will be assessed at each visit. Compliance will be assessed by counting returned tablets. The patient will be considered significantly noncompliant if he or she takes <80% or >120% of dispensed tablets. Deviations from the prescribed dosage regimen should be recorded in the electronic data capture (EDC).

7.7. Concomitant Therapy

Refer to the concomitant medications listed in the exclusion criteria (Section 6.2). Treatment with concomitant psoriasis therapies during the study is permitted as outlined below.

Patients will maintain their usual medication regimen for other concomitant diseases throughout the study unless specifically excluded in Section 6.2. Patients should be on stable doses of concomitant medications at baseline, and should remain at a stable dose throughout the study, unless changes need to be made for an AE. Additional systemic drugs are to be avoided during the study, unless required to treat an AE.

Use of non-live seasonal vaccinations and/or emergency vaccination (such as rabies or tetanus vaccinations) is allowed.

The following will be allowed as needed:

- use of topical antibiotics in the event of secondary infections of lesions;
- nonprescription shampoos;
- acetaminophen or aspirin; and

- topical moisturizers/ emollients on non-target lesions, bath oils, oatmeal bath preparations, and salicylic acid preparations. These topical agents should not be used within approximately 24 hours prior to visits requiring a PASI assessment.

Use of topical steroids of any potency is prohibited throughout duration of study.

Other medications may be allowed if approved by the sponsor or its designee. Patients will be instructed to consult the investigator or other appropriate study personnel at the site before taking any new medications or supplements.

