6.2. Exclusion Criteria

Patients will be excluded from study enrollment if they meet any of the following criteria. The timeframes included in the below criteria are relative to screening unless otherwise noted.

7. Are Eli Lilly and Company, PRCL Research Inc., or Contract Research Organization employees, investigator or site personnel directly affiliated with this study and the immediate families of either of these. Immediate family is defined as a spouse, parent, child or sibling, whether biological or legally adopted.
8. Are currently enrolled in any other clinical trial involving a study drug or off label use of a drug or device, or any other type of medical research judged not to be scientifically or medically compatible with this study. Patients who participated in the previous PRCL study (SMAD) will be allowed to be included in this study, provide that they meet all inclusion and none of the exclusion criteria.
9. Participated in a clinical study within 30 days (defined as the last dose of study drug), prior to first dosing in this study.
10. Present with pustular, erythrodermic psoriasis, generalized pustular psoriasis or acute guttate psoriasis.
11. Have current serious or unstable illnesses including hepatic, renal, gastroenterologic, respiratory, cardiovascular (including a history of ischemic or structural heart disease, conduction system disease or history of clinically significant arrhythmia), endocrinologic, neurologic, psychiatric, immunologic, hematologic, or dermatologic disease and other conditions that, in the investigator's opinion, could interfere with the analyses of safety and efficacy in this study.
12. Have a history of clinically significant severe drug allergies or severe post-treatment hypersensitivity reactions (including, but not limited to, erythema multiforme major, linear immunoglobulin A (IgA) dermatosis, toxic epidermal necrolysis, or exfoliative dermatitis).
13. Have received inactivated vaccine within 4 weeks prior to dosing in this study, or a live vaccine within 3 months prior to dosing in this study.
14. Present with a history of clinically significant opportunistic infection (e.g., invasive candidiasis or Pneumocystis pneumonia).
15. Had symptomatic herpes zoster within 3 months of randomization, other recent or ongoing infection that, in the opinion of the investigator, poses an unacceptable risk to participate in the study.
16. Present with any of the following laboratory test results:

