- Systemic psoriasis therapy (such as psoralen and ultraviolet A [PUVA] light therapy, cyclosporine, corticosteroids, methotrexate, oral retinoids, mycophenolate mofetil, thioguanine, hydroxyurea, sirolimus, azathioprine) or phototherapy (including ultraviolet B or self-treatment with tanning beds or therapeutic sunbathing) within 4 weeks prior to dosing in this study;
- Topical psoriasis treatment (other than moisturizing emollients) within 2 weeks prior to dosing in this study; or
- Any biologic agent within the following washout periods: 30 days for anti-TNF inhibitors and 90 days for others prior to dosing in this study.

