8.1. Discontinuation from Study Treatment

Discontinuation due to a hepatic event or liver test abnormality. Patients who are discontinued from using study drug due to a hepatic event or liver test abnormality should have additional hepatic safety data collected via EDC. Discontinuation of the study for abnormal liver tests **should be** considered by the investigator when a patient meets one of the following conditions after consultation with the sponsor designated medical monitor:

- ALT or AST >5X ULN
- ALT or AST >3X ULN along with one or more of the following criteria:
 - sustained for more than 2 weeks or
 - TBL >2X ULN or
 - prothrombin time >1.5X ULN or
 - the appearance of fatigue, nausea, vomiting, right upper-quadrant pain or tenderness, fever, rash, and/or eosinophilia (>5%)
- alkaline phosphatase (ALP) >3X ULN
- ALP >2.5X ULN and TBL >2X ULN
- ALP >2.5X ULN with the appearance of fatigue, nausea, vomiting, right quadrant pain or tenderness, fever, rash, and/or eosinophilia (>5%)

In addition, patients will be discontinued from the study drug in the following circumstances:

- White blood cell count $\geq 1.5X$ ULN or an increase in white blood cells above ULN and $>2X$ ULN from last predose measure
- Neutrophil or total lymphocyte count of $\geq 1.5X$ ULN or an increase in neutrophils or total lymphocytes above ULN and $>2X$ ULN from last predose measure
- Patient received concomitant medication listed in Exclusion Criteria
- Patient's failure to comply with protocol requirements or study-related procedures
- Termination of the study by the sponsor or regulatory authorities

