9.1. Efficacy Assessments

9.1.1. Primary Efficacy Assessment - Psoriasis Area and Severity Index (PASI)

Primary efficacy assessments will be based on the PASI.

The PASI is a proven and widely used tool to evaluate the severity of psoriasis (Hägg et al. 2017). The PASI scores the severity of disease on a scale from 0 to 72 (where a score of 72 indicates extreme disease severity) by combining assessments of extent of body-surface involvement in the head, trunk, arms, and legs together with the severity of desquamation, erythema, and plaque induration.

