10.3.3. Efficacy Analyses

10.3.3.1. Primary Analyses

Efficacy endpoints will be assessed using the ITT population.

The primary treatment effect will be measured as the difference between each active treatment arm and placebo in the percentage of patients with a $\geq 75\%$ improvement from baseline in PASI (PASI 75) at 12 weeks.

A one-sided Fisher's exact test with a 10% type 1 error rate will be used to compare each PRCL-02 treatment arm to placebo.

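### Protocol Sections 7.7 and 8.1 give conflicting instructions on salicylic acid and non-live vaccines, and the emollient limit in 7.7 cannot be applied to a whole-body PASI

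*Protocol*

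**What the plan says.** **Permission.** Protocol Section 7.7 first refers the reader to the exclusion list and then states: "Treatment with concomitant psoriasis therapies during the study is permitted as outlined below". Its as-needed list includes "topical moisturizers/ emollients on non-target lesions, bath oils, oatmeal bath preparations, and salicylic acid preparations". These topicals are to be withheld for about 24 hours before a PASI visit. The same section asks for stable doses of concomitant medication, asks patients to consult the site before taking anything new, and prohibits topical steroids. On vaccines it says: "Use of non-live seasonal vaccinations and/or emergency vaccination (such as rabies or tetanus vaccinations) is allowed".

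**Exclusion list.** Protocol Section 6.2, criterion 18, lists "Topical psoriasis treatment (other than moisturizing emollients) within 2 weeks prior to dosing in this study". Criterion 13 begins: "Have received inactivated vaccine within 4 weeks prior to dosing in this study". Both are written as windows before dosing.

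**Stop rule.** Protocol Section 8.1, in a list whose lead-in is mandatory, includes: "Patient received concomitant medication listed in Exclusion Criteria". It makes no reference to Section 7.7.

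**Endpoint.** Protocol Section 9.1.1 describes PASI as "combining assessments of extent of body-surface involvement in the head, trunk, arms, and legs together with the severity of desquamation", erythema and induration. SAP Section 2.13 computes it over the same four regions. SAP Section 2.7 counts a patient whose response cannot be determined because of missing data, early withdrawal included, as a non-responder.

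**The concern.** There are three linked problems.

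1. **Stop or continue.** A site that follows 7.7 keeps a salicylic acid user, or a patient given a seasonal vaccine, on study drug. A site that follows 8.1 literally stops the drug. The Schedule of Activities sends a patient who discontinues early to the end-of-study assessments, so a Week 12 PASI may not exist, and the SAP then scores non-response. Two patients with the same use and the same skin could receive different primary outcomes because their sites read different sections.

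2. **A lesion limit that cannot be applied.** Section 7.7 confines emollients to non-target lesions. The trial defines no target lesions, and every plaque in the four regions contributes to PASI. Protocol Section 6.3 sets a 24-hour emollient rule with no such distinction.

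3. **Unequal conditions at baseline and Week 12.** A non-emollient topical psoriasis product is washed out for 2 weeks before dosing but, if it is salicylic acid, may be in use by Week 12. The restraints are the hold of about 24 hours and the stable-dose and consult-the-site wording. Desquamation is one of the three PASI severity items, so a scale-reducing product could contribute to a measured improvement.

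**Working it through.** **Step 1. Set the passages side by side.**

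| Item | Section 7.7 | Section 6.2 | Section 8.1 read literally |
|---|---|---|---|
| Salicylic acid | Permitted as needed | Not named; falls under criterion 18 if it is a topical psoriasis treatment, as 7.7's own introduction suggests | Stop, on that reading |
| Non-live vaccine | Permitted | Inactivated vaccine named in criterion 13 (4 weeks before dosing) | Stop |
| Moisturizing emollient | Permitted, on non-target lesions | Expressly exempt in criterion 18 | No stop |

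The conflict covers the first two rows. It depends on 8.1 carrying the exclusion list into the treatment period. The bullet in 8.1 does this, because it can only concern patients already on study drug.

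**Step 2. Reproduce the planned power.** Inputs from Protocol Sections 10.1 and 10.3.3.1: 27 per arm; PASI 75 response 7.5% on placebo and 37.5% on active; 10% dropout scored as non-response; a one-sided Fisher's "exact test with a 10% type 1 error rate will be used to compare each PRCL-02 treatment arm to placebo".

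Exact power is the sum of Bin(x; 27, p0) × Bin(y; 27, p1) over all (x, y) whose one-sided hypergeometric p-value is at most 0.10.

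- No dropout, 7.5% v 37.5%: 0.882.
- With dropout, 0.9 × 7.5% = 6.75% v 0.9 × 37.5% = 33.75%: 0.842.

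The stated power of at least 80% is reproduced.

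**Step 3. Illustrate co-treatment.** The gains below are assumptions, added before dropout.

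| Assumed gain in PASI 75 | Rates after 10% dropout | Exact power |
|---|---|---|
| None | 6.75% v 33.75% | 0.842 |
| 2.5 points, both arms | 9.00% v 36.00% | 0.806 |
| 5 points, both arms | 11.25% v 38.25% | 0.774 |
| 2.5 points, placebo only | 9.00% v 33.75% | 0.754 |

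**Step 4. Illustrate the stop rule.** If sites applying 8.1 raise total non-responder imputation from 10% to 15% in both arms, the rates are 6.375% v 31.875% and power is 0.818. At 20% they are 6.0% v 30.0% and power is 0.791.

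**Step 5. How far can scale removal alone move PASI?** Within a region the score is (D + E + I) × A. Take D = E = I = s at baseline and A unchanged.

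- Baseline sum is 3s. Clearing D leaves 2s, a fall of 1/3 (33%).
- PASI 75 needs a sum of at most 0.25 × 3s = 0.75s. With D = 0, E + I must fall from 2s to 0.75s, that is 1.25/2 = 62.5%.

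Complete clearance of D thus lowers the required fall in E + I from 75% to 62.5%. It does not by itself produce a response.

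**The case against.** The best defence is that criteria 13 and 18 are eligibility windows and that 7.7, as the specific on-study permission, is naturally the exception to the general bullet in 8.1. That reading is reasonable, but neither document states it, and 7.7 itself opens by pointing back to the exclusion list. Criterion 18 also does not name salicylic acid, so that limb rests on how 7.7 introduces its list. The vaccine limb needs no such inference about the product, although vaccination has no stated link to PASI and reaches the endpoint only through a stop.

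The safeguards are real: the 24-hour hold, stable doses, consultation with the site, the ban on topical steroids, and the tabulation of concomitant medications in SAP Section 4.4. They limit co-treatment and make recorded use visible. They do not settle whether 8.1 applies.

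A reader might infer several stronger things that the documents do not support:

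- **That emollient use requires stopping study drug.** Criterion 18 exempts moisturizing emollients.
- **That co-treatment alone creates PASI 75 responders.** On the simple model in Step 5 it removes at most a third of the score, so it can only tip patients who are already close. Full clearance of scale, and its persistence through the 24-hour hold, are themselves assumptions.
- **That power collapses.** One or two extra placebo responders (11.2% or 14.9% v 37.5%) give 0.758 or 0.616, but only with no gain on active and with the planned dropout left out. The same 3.7 or 7.4 points in both arms, also without dropout, give 0.837 or 0.807. Heavier use on placebo is conjecture in a blinded trial.
- **That the trial is biased towards a positive result.** That would need greater use, or greater benefit from it, in the active arms, and nothing in the documents suggests either.

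**Conclusion.** The point holds in a limited form. Sections 7.7 and 8.1 give opposite instructions for non-live vaccines and, if salicylic acid is a topical psoriasis treatment as 7.7 implies, for salicylic acid too. The conflict can reach the primary endpoint through the non-responder rule, but only for a stopped patient who has no Week 12 PASI. The non-target-lesion limit has no meaning for this endpoint. Baseline and Week 12 PASI can be taken under different co-treatment conditions.

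The sample size is not wrong: 27 per arm gives exact power of 0.84 under the plan's own assumptions. The margin over 80% is small enough for modest effects to use it up, for example 5 points in both arms (0.77), 2.5 points in placebo only (0.75), or imputation rising to 20% in both arms (0.79). All three are illustrations, because the documents give no frequency of use, effect size or rate of stopping under 8.1. The amendment is worth making because it is cheap and concerns the primary endpoint, not because a loss of any given size has been shown.

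**What to change.** Make one protocol amendment with three wording changes:

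1. Reconcile Section 7.7, criteria 13 and 18, and Section 8.1, so that a single stated rule says whether items permitted by 7.7 fall under the 8.1 stop.
2. Remove the reference to non-target lesions in 7.7, or replace it with wording that applies to all PASI-scored skin, and align it with Section 6.3.
3. Reconcile the status of salicylic acid between the 2-week pre-dose washout and the on-study allowance, so that baseline and Week 12 PASI are taken under the same conditions.

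Which products are allowed, and when study drug is stopped, are for the sponsor to decide. The cost is the amendment itself, with no added visits or data, and possibly less freedom in skin care for patients, depending on the sponsor's choice.

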7.8. Treatment after the End of the Study

Not applicable.

8. Discontinuation Criteria

Patients discontinuing from the treatment prematurely for any reason should complete adverse event and other follow-up procedures per Section 2 of this protocol.

Patients discontinuing from the study prematurely for any reason must complete adverse event and follow-up procedures per Section 2 of this protocol.

